6. STUDY PROCEDURES

Upon presentation for cervical ripening, a non-stress test will be performed per BWH outpatient ripening protocol. Then a sterile vaginal exam will be completed to assign Bishop score, as per standard routine. A bedside ultrasound will be completed to confirm fetus is still in the vertex presentation. The patient will then be consented if they have a reactive non-stress test, a Bishop score <6 and cervical exam <3cm dilated with confirmed vertex fetus. Once the patient has been consented and randomized, the participant will have a Cook catheter or Dilapan-S by direct visualization with a speculum, For the Cook catheter, the uterine component of the balloon will be inflated to maximum 60mL, the vaginal balloon will not be inflated per standard practice at BWH and per the literature that shows slightly increased pain and negligible improvement in cervical ripening. The catheter will be taped to the inner thigh with gentle traction. For Dilapan-S, 3-5 dilators will be placed per BWH protocol.

After placement, the patient will be discharged home with strict return precautions per the BWH outpatient cervical ripening protocol. With written instructions of who to call/page, with phone number listed, list of concerns that should prompt calling / return to hospital: Fever > 100.4 Fahrenheit, labor, rupture of membranes, reduced fetal movement vaginal bleeding, what to do if the balloon/rods fall out, exact time and place to return. Patients must return to labor and delivery within 24 hours of cervical ripening agent placement at their scheduled inpatient induction time.

Upon return to labor and delivery, if not already expelled, the mechanical ripening device will be removed, and an examiner **blinded to the cervical ripening method** will complete a sterile vaginal exam to assign a Bishop score.

The patient satisfaction survey will be completed by the patient at this time in paper form and collected by study staff.

At that point health care providers will manage active labor per usual practice. Labor interventions are at the discretion of the healthcare provider. The need for operative delivery or cesarean section will be at the discretion of the healthcare provider.

Secondary outcome information will be obtained from the Epic record including delivery, maternal and neonatal outcomes as defined in the statistical analysis below.

If the patient satisfaction survey is not completed during the delivery admission, it may be collected anytime the patient returns to the hospital for routine prenatal care until the 6 week postpartum visit.

7. Risks and Discomforts

Women may experience discomfort with either Cook catheter or Dilapan-S insertion, though there is no increased risk from the standard BWH outpatient cervical ripening protocol.

Because both the Cook catheter and Dilapan-S are both routinely used for outpatient cervical ripening, we think that there is minimal increased risk from the study versus routine standard of care for outpatient cervical ripening.

8. Benefits

There is no direct benefit to individuals. There are however many benefits for the healthcare system in the future. By determining that Dilapan-S is noninferior to Cook catheter for outpatient cervical ripening we will be increasing provider awareness of an effective method of cervical ripening. Healthcare cost would benefit from the information gained in this study by potentially increasing outpatient cervical ripening which could decrease hospital stays. Currently, the most effective method of inducing labor remains unknown.

9. Statistical Analysis

The main outcome will be change in Bishop score. We will collect any information about outcomes regarding maternal or neonatal morbidity until four weeks from delivery. The patient satisfaction survey may be administered until the 6-week postpartum visit. Once these items are collected, patient participation will end.

Bishop score is defined by 5 components (Figure 3) all assessed during a sterile vaginal exam. These individual scores are then combined into a single score (0-13) to determine the Bishop score. Our

outcome of interest is change in Bishop score to be calculated as Bishop score after cervical ripening minus Bishop score prior to cervical ripening.

Figure 3. Bishop score. Final score is a sum of the 5 individual scores.

Score	Dilation (cm)	Position of Cervix	Effacement (%)	Station (-3 to +3)	Cervical Consistency
0	Closed	Posterior	0-30	-3	Firm
1	1-2	Mid-position	40-50	-2	Medium
2	3-4	Anterior	60-70	-1,0	Soft
3	5-6	--	80-100	+1 to +3	--

Secondary maternal outcomes will be measured including patient satisfaction with cervical ripening method via a survey administered after return to labor and delivery (Appendix B), cesarean delivery rate, time from admission on labor and delivery to delivery, maternal length of stay, and indication for cesarean delivery. We will also calculate a composite cervical ripening success score. Success will be defined by a lack of any of the following: failure of placement of cervical ripening agent, unscheduled return to medical care, rupture of membranes, vaginal bleeding, or need for further cervical ripening after the initial agent is removed. We will also calculate a composite maternal morbidity outcome. Morbidity will be defined by any of the following: higher-order laceration, blood transfusion, endometritis, wound infection, venous thromboembolism, hysterectomy, ICU admission or death. These outcomes will also be stratified by parity. We will also evaluate rates of regional analgesia use in both groups.

A composite neonatal morbidity will be calculated including any one of the following: culture-proven neonatal sepsis, neonatal blood transfusion, hypoxic-ischemic encephalopathy, intraventricular hemorrhage grade 3 or 4, or therapeutic hypothermia. We will also analyze NICU admission, NICU admission for greater than 48 hours, and neonatal length of stay.

This study design is a non-inferiority randomized control trial with 1:1 randomization comparing Dilapan-S to Cook Catheter with the primary outcome of change in Bishop score. We have defined a non-inferiority margin of 2 with a standard deviation of 3 consistent with prior literature. A Type I α error of 0.05 was selected. Assuming 80% power and a two-sided P value we would need 39 patients in each arm for a total of 78 patients; however, prior studies⁶ reported a 10% failure of placement rate (due to patient intolerance of exam or provider failure) to account for this and the small risk of loss to follow-up, we will increase the sample size by 15% and will include 45 participants in each group for a total of 90 participants.

For statistical purposes, intent to treat analysis will be performed. Non-parametric measures will be used for statistical analysis. These models will also be adjusted for parity.

10. Monitoring and Quality Assurance

The principal investigator will review the entries for each participant to ensure they are complete. We will not perform any interim analysis, as we feel there is minimal risk from the study protocol and would not stop the study early. When adverse events occur, they will be reported to the Partners' IRB within 5 days with a detailed description of the event as described in the guidelines for

adverse events reporting. Serious adverse events (severe hemorrhage, maternal death, neonatal death, neonatal hypoxemic encephalopathy) will be reviewed by the head of labor and delivery and the study staff to ensure the outcome is not related to the study protocol.

11. Privacy and Confidentiality

- Study procedures will be conducted in a private setting
- Only data and/or specimens necessary for the conduct of the study will be collected
- Data collected (paper and/or electronic) will be maintained in a secure location with appropriate protections such as password protection, encryption, physical security measures (locked files/areas)
- Specimens collected will be maintained in a secure location with appropriate protections (e.g. locked storage spaces, laboratory areas)- **No specimens collected**
- Data and specimens will only be shared with individuals who are members of the IRB-approved research team or approved for sharing as described in this IRB protocol
- Data and/or specimens requiring transportation from one location or electronic space to another will be transported only in a secure manner (e.g. encrypted files, password protection, using chain-of-custody procedures, etc.)
- All electronic communication with participants will comply with Mass General Brigham secure communication policies- **No electronic communication will occur**
- Identifiers will be coded or removed as soon as feasible and access to files linking identifiers with coded data or specimens will be limited to the minimal necessary members of the research team required to conduct the research
- All staff are trained on and will follow the Mass General Brigham policies and procedures for maintaining appropriate confidentiality of research data and specimens
- The PI will ensure that all staff implement and follow any Research Information Service Office (RISO) requirements for this research
- Additional privacy and/or confidentiality protections

12. References

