APPENDIX A: Brigham and Women's Outpatient Cervical Ripening Protocol

Medical Staff Note...

**OBSTETRICS AND GYNECOLOGY
BRIGHAM AND WOMEN'S HOSPITAL**

DATE: 12/21/2020 **Updated June 17, 2021** # 2313

TO: Medical Staff

FROM: [name], [name], [name], [name], [name],
[name], [name], [name]

RE: **Office-Based Ambulatory Cervical Ripening Protocols**

Updates June 17, 2021

GBS positivity is no longer an exclusion for office-based ambulatory cervical ripening using a mechanical method of cervical ripening, including Foley or Cook balloons, Dilapan or laminaria cervical dilators.

Mild polyhydramnios is not an exclusion for office-based ambulatory cervical ripening.

Well-controlled GDM, with or without medications, is not an exclusion for ambulatory office-based cervical ripening.

Background: As noted in a recent Medical Staff note from [name] (**Cervical Ripening and Induction of Labor in Nulliparous Patients before Forty Weeks' Gestational Age, #2304**) clinical practice

is evolving to increase the use of office-based ambulatory cervical ripening as the **initial step** for induction of labor in low-risk women from 39 weeks and 0 days gestation through 39 weeks and 6 days gestation. **One day of office-based ambulatory cervical ripening is an important part of a multi-step process that is followed by additional ambulatory (CWN5 Triage) or inpatient cervical ripening, if needed, and oxytocin induction of labor.**

At BWH we have years of experience with office-based ambulatory cervical ripening using oral misoprostol. Office-based ambulatory mechanical cervical ripening with a balloon catheter (Foley or Cook catheters) or Dilapan (hygroscopic cervical dilator) are also effective and safe methods (Alfirevic 2020, Dong 2020, Yang 2018, Saade 2019). Mechanical methods are particularly suitable for the office-based ambulatory setting as they are not generally associated with an increased risk of tachysystole.

The choice of office-based ambulatory cervical ripening agent is at the provider's discretion. However, we encourage the following:

- (1) First line: Balloon cervical ripening (30 cc Foley or Cook balloon)
- (2) Second line: Dilapan-hygroscopic cervical dilator
- (3) Third line: Oral misoprostol

At this time, we are not endorsing the use of dual agents in the office-based ambulatory setting (e.g. balloon or Dilapan plus misoprostol).

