Exclusions (all office-based ambulatory methods of cervical ripening):

Fetal conditions:

Contraindication to vaginal delivery (non-vertex presentation, complete placenta previa, etc.)
IUGR: Growth < 5th percentile
Abnormal umbilical artery dopplers
Oligohydramnios or polyhydramnios (**mild polyhydramnios is not an exclusion to ambulatory office-based cervical ripening**)
Multiple gestation
Major fetal anomalies
Induction for the indication of non-reassuring fetal assessment
Any history of decreased fetal movement
Any history of non-reassuring fetal assessment

Maternal conditions:

Prior Caesarean delivery or uterine surgery involving removal of a full thickness of uterine tissue
Clinically significant vaginal bleeding.
Type 1 or Type 2 diabetes mellitus. (**Well-controlled GDM with or without medication is not a contraindication to ambulatory office-based cervical ripening.**)
Significant hypertension: preeclampsia, or taking antihypertensive medications instituted or recently up-titrated in this pregnancy to control blood pressure.
A patient who is unable to understand instructions or return easily should symptoms arise

Exclusion specific to mechanical methods (Foley/Cook/Dilapan):

GBS positivity is no longer an exclusion to office-based ambulatory cervical ripening using a mechanical method of cervical ripening, including Foley or Cook balloons, Dilapan or laminaria cervical dilators.

Protocol: Overall, office-based ambulatory cervical ripening by any method should be followed by additional CWN5 triage cervical ripening, if needed, or by inpatient induction of labor if the cervix is favorable within 6 to 24 hours.

Important guidance: An inpatient induction of labor slot should be booked for 6 to 24 hours following the initiation of office-based ambulatory cervical ripening.

Prior to ripening (all methods):

- 1) Confirm eligibility. Review exclusion criteria above.
- 2) **Confirm that an inpatient induction slot is booked at 6 to 24 hours following the initiation of office-based ambulatory cervical ripening.**
- 3) Confirm that clinical testing such as NST or BPP is performed within the appropriate time frame (i.e. if weekly fetal testing is indicated, this should be performed within the week prior to the induction or if an ultrasound estimate of fetal weight is indicated this should be performed within 2 weeks of the induction).

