- 4) Confirm cephalic presentation and normal fluid volume. This can be done via formal or bedside ultrasound. If a formal ultrasound is performed within the week but not on the day of induction, cephalic presentation should be confirmed by physical exam or bedside ultrasound.

Prior to ripening (misoprostol only):

- 1) NST must be performed and must be reactive without excessive uterine activity (no more than 2 contractions in 10 minutes).

Foley Balloon Placement:

- 1) This can be placed in any setting, though ideally in the office-based ambulatory setting in the afternoon.
- 2) Either a 30 cc Foley (inflated up to 35 cc) or a Cook catheter can be used.
- 3) Balloons can be placed digitally or with a speculum (at provider discretion). If a speculum is used, the cervix should be cleansed with betadine prior to placement.
- 4) Only 2 attempts at a balloon should be performed. If placement fails after 2 attempts, the provider can place Dilapan instead or abandon office-based ambulatory mechanical ripening.
- 5) After placement, the Foley catheter tail can be taped to the thigh, tucked into the vagina or tied off and trimmed.
- 6) No monitoring is needed after placement.
- 7) If the Foley catheter falls out before the scheduled inpatient appointment, the patient should be instructed to throw out the Foley catheter. She can stay home until her scheduled appointment (unless labor, rupture of membranes or other concerns require an office or hospital visit).

Dilapan Placement:

- 1) Cervix is visualized with a speculum and cleansed with betadine.
- 2) Dilapan rods are placed using a ring forceps. Ideally 3-5 rods should be placed. No more than 5 rods should be used. Rods can be moistened with saline or sterile water to aid in placement.
- 3) A moistened gauze can be placed in the vagina to help keep the Dilapan in place if desired (though not necessary).

- 4) The number of Dilapan and gauzes left in the patient should be clearly documented in the EPIC record.
- 5) No monitoring is needed after placement.
- 6) If the Dilapan(s) or sponge(s) fall out before the scheduled inpatient appointment, the patient should be instructed to collect all the rods/sponges in a plastic bag or take a picture of the rods/sponges and throw them away. She can stay home until her scheduled appointment (unless labor/rupture of membranes or other concerns arise).

Misoprostol Placement:

- 1) 50 mcg of oral misoprostol is administered

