Appendix B: Patient Satisfaction Survey

Patients: Please consider your experience with cervical ripening, from when the device was placed until now. The answers to your questions will not affect any aspect of your care.

1. Before placement of the cervical ripening device were you anxious? (Please circle one)

1- Not at all 2- Slightly 3- Moderately 4- Very 5- Extremely

2. Did the insertion of the device cause you any discomfort? (Please circle one)

1- Not at all 2- Slightly 3- Moderately 4- Very 5- Extremely

3. What number would you rate the pain you had while the device was being placed? (scale 0-10, 0= no pain, 10= worse pain imaginable, please circle one number)

0 1 2 3 4 5 6 7 8 9 10

4. Once you went home with cervical ripening device (please circle one for each question):

A) Did you feel any discomfort?

1- Not at all 2- Slight Discomfort 3- Moderate Discomfort 4- Very Uncomfortable 5- Extremely Uncomfortable

B) Were you able to complete your routine daily activities?

1- Not at all 2- Slightly 3- Moderately 4- Very 5- Extremely

C) How able were you to get some sleep?

1- Not at all 2- Slightly 3- Moderately 4- Very 5- Extremely

5. Please rate your overall discomfort during the entire cervical ripening experience (scale 0-10, 0= no pain, 10= worse pain imaginable, please circle one number).

0 1 2 3 4 5 6 7 8 9 10

6. Please rate your overall satisfaction with the entire cervical ripening experience(scale 0-10, 0= completely dissatisfied, 10= completely satisfied, please circle one number).

0 1 2 3 4 5 6 7 8 9 10

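### The Aim 2 survey rates ripening up to the moment of completion, so its two overall ratings can cover further ripening on late forms that on-time forms cannot include

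*Combined protocol and SAP*

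**What the plan says.** The lead-in in Appendix B sets the rated period: "Please consider your experience with cervical ripening, from when the device was placed until now". Item 6 then asks: "Please rate your overall satisfaction with the entire cervical ripening experience". Item 5 uses the same scope for discomfort. Neither item names an end event.

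Sections 3 and 6 plan one completion time: return to Labor and Delivery, once the device is out and the blinded exam is done, before further labor management. Section 6 adds a fallback. It opens with the condition "If the patient satisfaction survey is not completed during the delivery admission" and continues that "it may be collected anytime the patient returns to the hospital for routine prenatal care until the 6 week postpartum visit". Section 9 repeats it: "The patient satisfaction survey may be administered until the 6-week postpartum visit". This permits late answering, not only late pick-up of a form already filled in.

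Ripening may continue after return. Appendix A describes the ambulatory day as "an important part of a multi-step process that is followed by additional ambulatory (CWN5 Triage) or inpatient cervical ripening, if needed". Section 9 treats a need for more ripening once the first agent is out as a failure on the success composite.

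Section 9 lists satisfaction with the ripening method as a secondary outcome. It specifies intent to treat, non-parametric methods and adjustment for parity. It gives no rule for late forms and no analysis by time of completion.

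**The concern.** Women following the plan exactly can rate different periods. On a form completed as planned, the rated period ends just after device removal and the exam. On a late form it ends days or weeks later, and any further ripening falls inside it. Item 6 is the only satisfaction rating on the form, so it is the likely measure for Aim 2, although no section names it as the endpoint.

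At stake is a clean reading of Aim 2, one of the trial's two specific aims. Mixed rating periods and longer recall add noise. They could also bias the comparison if late completion, or the further ripening that late forms pick up, is more common with one device. Without a completion time, the late forms could not be separated afterwards.

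**Working it through.** The plan gives no figure for satisfaction: no power, no standard deviation and no expected share of late forms. Its sample size (39 per arm, raised to 45) is for change in Bishop score and does not bear on this point. The check is therefore mainly a reading of the text, followed by an illustration.

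**1. Which ratings lack a fixed end?** The form has 8 ratings: items 1, 2, 3, 4A, 4B, 4C, 5 and 6. The first 6 are tied to before placement, placement, or time at home. For those, lateness mainly adds recall error. The other 2 (items 5 and 6) have no end point.

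**2. What does each form cover?**

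| | Planned form | Late form |
|---|---|---|
| Completed | On return, after removal and exam | After birth within the admission, or up to the 6-week visit |
| Time since placement | About 24 hours or less (return is within 24 hours) | Up to about 6 weeks after birth |
| Device removal | Included | Included |
| Further ripening after return | Not possible, not yet happened | Can be included |

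The fallback condition refers to the whole delivery admission, so a form completed after birth but before discharge also fits the wording. Appendix A sets the return time: "An inpatient induction of labor slot should be booked for 6 to 24 hours following the initiation of office-based ambulatory cervical ripening".

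**3. How many women?** The rated events differ only for women who both answer late and had further ripening. Assume 10% late and 30 to 50% of those with further ripening:

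- 90 × 0.10 × 0.30 = 2.7
- 90 × 0.10 × 0.50 = 4.5

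That is about 3 to 5 of 90 women.

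**4. How large could a bias be?** Suppose further ripening lowers item 6 by 1 to 2 points (assumed) in those women only. Then bias = difference in late share × share with further ripening × shift.

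- Equal late shares, equal further ripening: bias 0.
- 10% v 30% late: 0.20 × 0.30 × 1 = 0.06 to 0.20 × 0.50 × 2 = 0.20 points.
- Equal 10% late, further ripening 30% v 50%: 0.10 × 0.20 × 1 = 0.02 to 0.10 × 0.20 × 2 = 0.04 points.

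**5. A broader illustration.** Simulations (40,000 trials per setting, 45 per arm, rank test, SD 2 or 3) lowered *every* late form by 1 to 2 points, so they mix recall and birth effects with further ripening. With 10 to 30% late in both arms, power fell from an assumed 80% to between 73% and 80%. At 10% late in both arms the error rate was 5.0 to 5.1%. With 10% v 20 to 30% late, bias was 0.1 to 0.4 points and the two-sided 5% error rate became 5.4 to 13.2%. None of these inputs comes from the documents.

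**The case against.** The strongest reply is that the plan does fix one time for every form, and the later window is only a fallback against missing data. That is largely right, and it is why the affected group is probably small. The fallback is nevertheless written into two sections, with no rule for the forms it produces.

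A reader might infer that late forms rate labor and birth. The wording does not support that: the lead-in and items 5 and 6 name cervical ripening. Birth may color an answer, but it is not what is asked.

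A reader might also take the 13% error rate as a finding. It needs a 20-point gap in late share, a 2-point shift and an SD of 2 together, and nothing in the documents suggests such a gap. With a 5-point gap the error rate was about 5.0 to 5.8%. The 80% baseline is also assumed, since Aim 2 has no power target.

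The 10% placement failure cited in Section 9 (0.10 × 90 = 9 women) might be counted as affected. It concerns the start of the rated period, not its end. It is also an upper bound, because Section 3 and Appendix A allow another method after a failed placement.

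Finally, the documents reproduce the survey questions but no case report forms. They do not show that staff fail to note collection dates, only that no such record is specified.

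Further ripening that follows from the assigned device may be a legitimate part of satisfaction under intent to treat. The difficulty is that only late forms can include it.

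**Conclusion.** The point holds in a limited form. Items 5 and 6 have no fixed end, and the permitted completion window lets late forms include further ripening that on-time forms cannot. Late forms also carry longer recall.

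The size cannot be established from the documents and is probably small. The expected harm is noise in a secondary outcome. Between-arm bias arises only if late completion or its effect differs by arm, and the documents give no evidence either way. The reading that Aim 2 is biased or invalid is not supported. The Bishop score comparison and the sample size are untouched. The case for a change rests on its low cost.

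**What to change.** Give the lead-in and items 5 and 6 one end point that matches the planned survey time, for example: *from the start of your cervical ripening appointment until the device was removed or confirmed out and you had your first exam on return to Labor and Delivery*. Ending at arrival would be worse, because it would drop device removal, which on-time forms now cover. The proposed wording also suits women with failed placement, and women whose device fell out early, of whom Appendix A says "She can stay home until her scheduled appointment".

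In addition:

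- Put a completion date and time on the form.
- Keep the late window, and keep all completed forms in the intent-to-treat analysis.
- Report the number of post-delivery forms by arm.
- Add a sensitivity analysis limited to pre-delivery forms. It selects on a post-randomization event, since women who labor quickly may have less chance to finish the form before delivery. It should support the main analysis, not replace it.

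The cost is a small revision of a paper form and one extra analysis. If enrollment has begun, the form version must be recorded. Because the new end point matches the planned completion time, existing on-time forms and revised forms would cover nearly the same period.

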Our study population will include women 18-50 years of age at term (37-41 6/7 weeks gestational age) who are low risk (i.e. without any maternal or fetal co-morbidity) and with a singleton gestation in cephalic presentation who are candidates for outpatient cervical ripening per the Brigham and Women's outpatient cervical ripening protocol (Appendix A). Both nulliparous and multiparous women will be included. Women will need to have a bishop score <6 or cervical dilation <2cm with intact membranes to be included, as these are the women currently being offered outpatient cervical ripening prior to labor induction. Women will be excluded if there is a contraindication to outpatient cervical ripening per Brigham and Women's outpatient cervical ripening protocol (Appendix A) or contraindication to vaginal delivery. Women with history of a prior cesarean section will be excluded given their management may differ after cervical ripening. Non-English-speaking women will also be excluded given lack of study staff ability to communicate in languages other than English and lack of guaranteed 24/7 interpreters. Women who are patients of study investigators will be eligible for enrollment. This vulnerable population will be protected from coercion by giving patients a consent form to review at home prior to actual study enrollment and by encouraging patients to discuss the study with other healthcare professionals.

Women will be recruited from all practices that deliver at the Brigham, including Maternal Fetal Medicine, general Obstetrics clinics, private practice groups, and midwifery groups at Brigham and Women's Hospital. By recruiting from all of the delivering groups at BWH, we should be enrolling a diverse patient population.

5. Subject Enrollment

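### The neonatal morbidity composite omits death, so a neonatal death without a listed item would count as no event in the planned comparison between arms

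*Combined protocol and SAP*

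**What the plan says.** Section 9 (Statistical Analysis) counts a neonatal composite event when any one of these is present: "culture-proven neonatal sepsis, neonatal blood transfusion, hypoxic-ischemic encephalopathy, intraventricular hemorrhage grade 3 or 4, or therapeutic hypothermia". The list is closed, and no other part of the document adds to it.

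The same section defines a maternal morbidity composite whose list ends with "venous thromboembolism, hysterectomy, ICU admission or death".

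Three further neonatal outcomes follow: "We will also analyze NICU admission, NICU admission for greater than 48 hours, and neonatal length of stay". The analysis rules are intention to treat, adjustment for parity, and one sentence on method: "Non-parametric measures will be used for statistical analysis". None of them mentions infants who die.

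On data, Section 6 (Study Procedures) says "Secondary outcome information will be obtained from the Epic record including delivery, maternal and neonatal outcomes as defined in the statistical analysis below", and Section 9 sets the window: "We will collect any information about outcomes regarding maternal or neonatal morbidity until four weeks from delivery".

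Neonatal death is named only in Section 10 (Monitoring and Quality Assurance), in the list that begins "Serious adverse events (severe hemorrhage, maternal death, neonatal death, neonatal hypoxemic encephalopathy". Those events are reviewed by the head of labor and delivery and the study staff. Adverse events in general go to the IRB within 5 days.

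**The concern.** A harm composite should not score the gravest outcome as its absence. Under the rule as written, an infant who dies with one of the five items is counted, but an infant who dies without any of them is scored the same as a healthy infant.

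The other neonatal outcomes may not pick the death up. If it came before any NICU admission, both NICU outcomes would be negative. Its length of stay would be short, and with no rule for deaths that stay could be ranked as a good result.

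At stake is whether the planned comparison of neonatal harm between the two devices is complete. The non-inferiority conclusion on the Bishop score is not involved.

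**Working it through.** The plan gives no figure for any neonatal outcome, so there is none to reproduce. The check compares the relevant texts and then sizes the effect.

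**Texts side by side**

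1. Neonatal composite (Section 9): five items, death absent.
2. Maternal composite (Section 9): death present, under the same label of morbidity. The label therefore does not explain the omission.
3. Serious adverse events (Section 10): two neonatal events are named, death and encephalopathy. The composite includes encephalopathy but not death.
4. Outcome data (Section 6): taken from the Epic record as Section 9 defines them, and Section 9 defines no neonatal death outcome.

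**Denominator**

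Section 9 inflates 39 per arm by 15%: 39 × 1.15 = 44.85, rounded to 45, or 90 in total. Pregnancies are singleton (Section 4), so there are up to 45 infants per arm. The sample size rests on the Bishop score margin of 2 and SD of 3. No neonatal outcome enters it.

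**How likely is a neonatal death?**

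The documents give no rate. For an assumed rate r per birth, P(at least one in 90) = 1 − (1 − r)^90:

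| Assumed r | Expected deaths (90r) | P(at least one) |
|---|---|---|
| 0.02% | 0.018 | 1.8% |
| 0.1% | 0.09 | 8.6% |
| 0.5% | 0.45 | 36% |

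At each assumed rate this is an upper limit on the chance of a missed death, because a death with a listed item is already counted. The documents give no basis for the share of deaths without a listed item, so none is applied.

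**Effect on the composite of one missed death, with no other events**

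- The arm's rate becomes 0/45 instead of 1/45, a change of 2.2 percentage points.
- Exact 95% interval for 0/45: upper limit 1 − 0.025^(1/45) = 7.9%, so 0 to 7.9%. For 1/45 it is 0.06% to 11.8%.
- Fisher's exact test, 1/45 against 0/45: the single event is equally likely to fall in either arm, so two-sided p = 0.5 + 0.5 = 1.0.
- For k events against none, p = 2 × C(45,k)/C(90,k). This gives 0.056 for k = 5 and 0.026 for k = 6, so six against none would be needed to reach p < 0.05.

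**Effect on length of stay of one early death**

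This assumes an unadjusted rank-sum test of 45 against 45, with the death ranked either best or worst.

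- Moving the infant from rank 1 to rank 90 adds 89 to its own rank and takes 1 from each of its 44 arm-mates. The rank sum changes by 89 − 44 = 45, and the arm's mean rank by 45/45 = 1.00.
- Without ties, the SD is √(45 × 45 × 91/12) = 123.9, so z moves by 45/123.9 = 0.36. Against leaving the infant out, the shift averages about half of that, 22.5/123.9 = 0.18.
- Stays in whole days would be tied, which shrinks the SD: variance = (45 × 45/12) × [91 − Σ(t³ − t)/(90 × 89)], where t is the size of each tied group. If the other 89 infants fall into tied groups of 45, 30 and 14 (assumed), Σ = 120,780, SD = 113.2 and z moves by 0.40. With groups of 70, 15 and 4 (assumed), Σ = 346,350, SD = 89.8 and z moves by 0.50.

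The parity-adjusted analysis in the plan may give somewhat different values.

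**The case against.** The strongest reply is that the plan already handles a neonatal death. It is a named serious adverse event, it is reviewed individually, and it is reported to the IRB. That is right, and a reader who inferred that a death would disappear from the trial would be wrong. What remains is narrower: Section 10 asks whether the event was related to the protocol and does not compare arms. The document plans no by-arm table of adverse events of any kind, so nothing else supplies the comparison.

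Three stronger readings are tempting, and the documents do not support them.

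- *An early death will rank as a good length of stay.* The plan is silent. An analyst could enter the observed stay, exclude the infant, or rank the death worst. The favourable rank is possible, not prescribed, and a later death after a long stay would not raise the problem. Maternal length of stay has the same gap for a maternal death.
- *A fetal death after device placement would go unreported.* Fetal death is neither a listed outcome nor in the serious adverse event list. But the sentence in Section 10 on reporting adverse events is general and not confined to that list, and the composite at issue is neonatal. This supports only a request to show any such death by arm.
- *The omission could change a result.* One death cannot move the composite test, and the no-tie shift of 0.36 in z, although not a ceiling once stays are tied, stays modest in the examples above.

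The reply that a morbidity composite need not include death fails, because the plan's own maternal morbidity composite does.

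**Conclusion.** The point holds as a free or cheap improvement. The closed list in Section 9 would score a neonatal death without a listed item as no event, in contrast to the maternal composite beside it, and no by-arm reporting of deaths fills the gap. That much follows from the text with no assumption. The length-of-stay part is weaker: it is a missing rule, and an early death could, but need not, look favourable.

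The practical size is small. The outcome is secondary, and enrolment is limited to women who are "low risk (i.e. without any maternal or fetal co-morbidity) and with a singleton gestation", at term, so deaths should be rare. How rare is an assumption, because the documents give no rate. The reason to act is complete reporting of harm, and a rule set before any death is known.

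**What to change.** In Section 9:

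1. Add neonatal death, up to the existing limit of four weeks from delivery, to the neonatal composite. The maternal composite shows that the label can stay.
2. State that any fetal or neonatal deaths will be reported by arm.
3. State how deaths enter the neonatal length-of-stay analysis, for example as the worst rank, or as an analysis of survivors with deaths shown by arm. The same sentence could cover maternal length of stay.

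The cost is a few lines of wording, with no extra participants or visits and no change to the primary analysis or sample size. The one small burden is that deaths after discharge or at another hospital may need checking beyond the Epic delivery record.
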